12/23	19-24	Plasma conc and DNA Analyses; Summary Variables and Statistical Analyses; Manuscript finalization and submission; Final IRB, DSMB and IRB reviews; Draft R01 Phase 3 submission if warranted.	25= target			

INCLUSION AND EXCLUSION CRITERIA

Figure 6: Inclusion and Exclusion Criteria						
Inclusion Criterion	Rationale					
Ages 18-49 years	Age of adult childbearing persons					
Singleton pregnancy	Appropriate for initial Phase 2 trial					
Inpatient or outpatient status	Target is pregnant persons with refractory sNVP					
Care within Prentice Women's Hospital maternity practices	Retain subjects through pregnancy; coordinate with obstetrical care					
English speaking	Measures in English, staff are English speaking					
Obstetrician's evaluation and diagnosis of sNVP or HG	Differentiate from medical disorders (i.e. pancreatitis, appendicitis)					
Tolerance of oral disintegrating tablet at bedtime	Preparation is appropriate for persons experiencing emesis					
PUQE score of 10-15; moderate/high or severe	Pharmacotherapy is appropriate for this level of severity					
Refractory sNVP	Inadequate response to two commonly used drugs					
Anti-emetics may be continued as in real-world practice	Focus is mirtazapine for sNVP non-responsive to other medications					
Exclusion Criterion	Rationale					
Allergic or adverse reaction to mirtazapine	Inappropriate treatment					
Patient has bipolar disorder without anti-manic drug treatment	Risk for hypomania/mania induction					
Subjects with active depression, or history of or current active suicidal ideation or attempt	Mitigate risk for suicidality					

VULNERABLE POPULATIONS

The disease studied, sNVP, is specific to pregnant individuals. Case series studies of pregnant persons with sNVP or HG and who were treated with mirtazapine are reviewed in the Research Strategy section. Mirtazapine is FDA-indicated for the treatment of depression, and data on reproductive outcomes are available from treatment of this group of people. Additional information on pregnancy outcomes and neonates will be collected from the delivery record.

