Endeavor to Stop Nausea/Vomiting Associated with Pregnancy (E-SNAP) NCT05452174 09/30/2020

STATISTICAL DESIGN AND POWER ANALYSIS

Our data management team includes a highly experienced clinical trials statistician and database programmer. The REDCap management system was developed and functioning at Northwestern and is being transferred via a DUA. We are mindful of subjects' time and we send links to allow women to enter self-report measure data from home (for example, for recording of daily PUQE scores).

Analytic Approach. Descriptive statistics such as demographic and baseline clinical information will be summarized for all eligible women. These results will inform the feasibility, design and statistical approach for construction of the subsequent randomized controlled trial if the findings from the proposed study demonstrate the acceptability and feasibility of the protocol. This R21 study is not expected nor intended to have the power to address the outcomes described below, but to provide data to guide the design of a phase 3 RCT.

Aim 1. Define acceptability of mirtazapine for refractory NVP. Acceptability is defined by the number of women who accept participation compared to the total who undergo the consent procedure. All women will be asked for the reason behind their decision. A standard consort chart¹ will be created to record subject flow through the protocol. The acceptability of mirtazapine for NVP/HEG is a factor in the feasibility of the eventual RCT and is an important factor in the ability to recruit subjects and define the number of sites required.

Aim 2. Determine the tolerability and safety of the dosing regimen. Measures of tolerability include the proportions of: 1) emergent side effects on the ASE, which will be isolated by comparison to symptom ratings at intake; 2) withdrawals attributable to side effects; and 3) women who elect to continue mirtazapine after the initial 3-week trial. The daily PUQE scores will be used to evaluate the time (in days) to remission during the 3 week trial. We will use Kaplan-Meier curves to visualize time to remission (defined by a PUQE score of 3 or 4. Additionally, we will fit Cox regression models to identify factors that may be associated with time to remission.

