Sample Size Considerations. The proposed study is not powered nor expected to evaluate the efficacy of mirtazapine for sNVP. To estimate a preliminary sample size for the efficacy of mirtazapine for NVP/HEG for the initial 3 week trial, we will assume 80% power, two-sided significance=.05, and a standard deviation of 2.1 (derived from Koren et al⁴), and a moderately severe PUQE score (\approx 10) at study entry. The standard deviation of the change in PUQE scores from baseline to week 3 is conservatively estimated to be 2.97 by assuming that the correlation is zero. With 20 subjects, we can detect a 23% reduction in mean symptom scores (a 2.3 point decrease in PUQE scores). Based on the case studies, we anticipate a more favorable symptom reduction than 2.3 points. To allow a 20%

dropout rate, we will enroll 25 subjects. We enrolled 2 participants, who completed the 3- week study at Northwestern, before the study was closed.

References.

- 1. Trials CTRo. The CONSORT Flow Diagram. Accessed.

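### The SD of change of 2.97 is labelled conservative but rests on an unstated equal-SD assumption, and the stated 2.3-point detectable change does not follow from the stated inputs

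*SAP*

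**What the plan says.** Under Sample Size Considerations the SAP assumes "80% power, two-sided significance=.05, and a standard deviation of 2.1", the SD being borrowed from a cited placebo-controlled trial of another drug, with "a moderately severe PUQE score" of about 10 at entry. The SD of the change from baseline to week 3 is "conservatively estimated to be 2.97 by assuming that the correlation is zero". It then states: "With 20 subjects, we can detect a 23% reduction in mean symptom scores", which it equates to "a 2.3 point decrease in PUQE scores". It adds: "Based on the case studies, we anticipate a more favorable symptom reduction than 2.3 points". Allowing for 20% dropout, 20 becomes 25 enrolled.

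Two other places bear on the spread of scores. Protocol Figure 6 requires a "PUQE score of 10-15; moderate/high or severe" at entry. SAP Aim 2 analyses time to remission, "defined by a PUQE score of 3 or 4", and the Protocol's Mirtazapine Regimen paragraph uses the same definition.

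The SAP says, both in its Analytic Approach and under Sample Size Considerations, that the study is not powered for efficacy. The Protocol's Objectives say the study will inform sample size estimation for the later randomised trial.

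**The concern.** Zero correlation is a cautious choice about the correlation, provided the true value is not negative. It gives no protection if scores are more variable at week 3 than at entry. This trial selects women within a six-point band at the upper end of the scale and hopes to move some of them to the bottom. If some remit and others do not, week-3 scores become a mixture that can be much wider than the entry distribution. A figure labelled conservative would then be too small.

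At stake are the accuracy of the stated detectable change and the risk that a later planner treats 2.1 or 2.97 as a safe value because the SAP calls it conservative.

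**Working it through.** **1. The plan's own figures.** For a change score, SD of change = √(s₀² + s₃² − 2·r·s₀·s₃). With s₀ = s₃ = 2.1 and r = 0 this is 2.1 × √2 = 2.97, which reproduces. Enrolment of 20/(1 − 0.2) = 25 also reproduces.

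**2. The detectable change.** This is a one-sample (paired) test with n = 20, two-sided 0.05 and 80% power.
- Normal approximation: 2.97 × (1.960 + 0.842)/√20 = 1.86.
- Noncentral t, 19 df: 0.660 × 2.97 = 1.96.

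The stated 2.3 does not reproduce. At SD 2.97, power for 2.3 points is 91%, and 80% power would need only 14 (z) or 16 (t) subjects. The nearest match found is 90% power by t-test, which gives 2.27.

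**3. How much slack 2.3 carries.** 2.3/0.660 = 3.48, so 2.3 is detectable with 80% power up to an SD of change of 3.48. With s₀ = 2.1 that allows a week-3 SD of up to 2.78 (r = 0), 3.35 (r = 0.25) or 4.02 (r = 0.5).

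**4. What the entry and remission scores could imply.** The documents give no remission rate, week-3 SD or correlation, so everything in this step is an assumption. Take entry mean 12 and SD 1.6; remitters evenly split between 3 and 4 (mean 3.5, variance 0.25); and non-remitters falling f points on average with SD 2.1 around that. With remission share p:

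Var(change) = p(1.6² + 0.25) + (1 − p)(2.1²) + p(1 − p)(8.5 − f)²

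For p = 0.5 and f = 0: 1.405 + 2.205 + 18.06 = 21.67, so SD = 4.66.

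SD of change, with the detectable change at n = 20 (0.660 × SD) in brackets:

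| Remission | f = 0 | f = 2 | f = 4 |
|---|---|---|---|
| 10% | 3.28 (2.16) | 2.84 (1.87) | 2.46 (1.63) |
| 20% | 3.96 (2.61) | 3.29 (2.17) | 2.71 (1.79) |
| 50% | 4.66 (3.07) | 3.76 (2.48) | 2.94 (1.94) |
| 80% | 3.83 (2.53) | 3.14 (2.08) | 2.52 (1.67) |

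Simulating whole-number PUQE scores lowers the f = 0 column slightly, to 3.15, 3.85, 4.55 and 3.73. The other columns barely move.

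So 2.97 is exceeded in most cells with f between 0 and 2 and in none with f = 4. The 3.48 limit is exceeded in four of the twelve cells: f = 0 with 20%, 50% or 80% remission, and f = 2 with 50%.

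**5. Power for 2.3 points at n = 20.** It is 91% at SD 2.97, 80% at 3.48, 66% at 4.1 and 58% at 4.5.

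**The case against.** The strongest reply is that the stated 2.3 is not optimistic on the plan's own inputs. It is pessimistic by about a third of a point, and that margin absorbs a moderate rise in the week-3 SD. This stands.

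The wide spread also depends on non-remitters hardly improving, which no passage says. Doses escalate weekly, other anti-emetics may continue, and the Protocol notes that nausea and vomiting often resolve by mid-gestation, so partial improvement is plausible. An average fall of about 4 points in non-remitters brings the SD of change below 3. A positive correlation helps too: at r = 0.5 and baseline SD 2.1, the SD of change stays within 2.97 up to a week-3 SD of about 3.4. These points stand as well.

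Where the SD is largest, the mean fall is also large. At 50% remission with no change in the rest it is 0.5 × 8.5 = 4.25 points, above the detectable 3.07. Low power for 2.3 points at that SD pairs a small effect with the spread of a larger one.

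A reader might therefore infer three things that the documents do not support:
- that the week-3 SD will be about twice 2.1, although they give no figure for it;
- that 2.3 is optimistic in general, which is true only above an SD of change of 3.48;
- that the phase 3 trial would be undersized, although no passage carries 2.1 or 2.97 into its planning.

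None of this rescues the label. Zero correlation alone does not make 2.97 conservative, and the second assumption behind it is neither stated nor justified.

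**Conclusion.** The concern holds in a limited form. The SD of change of 2.97 depends on an unstated equality of SDs at baseline and week 3, and the trial's own entry and remission scores make that equality doubtful. Under the stated illustrative assumptions the SD of change could lie anywhere from about 2.5 to about 4.5, so 2.97 is a mid-range value and not a bound. Separately, and without any assumption about remission, 2.3 points does not follow from the SAP's inputs, which give 1.96 (t) or 1.86 (z).

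The consequence for this trial is minor. Efficacy power is expressly disclaimed, and the SAP reports closure after 2 enrolled participants. The point matters mainly for anyone who reuses the planning figures. If the true SD of change were 4.1–4.5, a change-score design sized on 2.97 would need (4.1/2.97)² to (4.5/2.97)², or about 1.9 to 2.3 times, as many women. That is conditional on a reuse the documents do not plan.

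**What to change.** In the SAP's Sample Size Considerations:
- Delete the word *conservatively* and say that 2.97 assumes zero correlation and an SD of 2.1 at both baseline and week 3.
- Reconcile 2.3 with 1.96: either give 1.96 for 80% power, or state the power or other input that produces 2.3.
- Report the detectable change at n = 20 and 80% power over a range of SDs of change: 1.98 points at 3.0, 2.31 at 3.5, 2.64 at 4.0 and 2.97 at 4.5.
- For phase 3 planning, set the week-3 SD and the baseline-to-week-3 correlation separately, and do not carry 2.1 forward as the week-3 SD. Two completers cannot supply these values, so their source should be named.

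The cost is wording only, with no extra participants or data. The downside is that the upper end of the range looks less favourable than the single figure now given.

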Physiology of Emesis. Vomiting is a complex neuromuscular cascade of events coordinated by the central and autonomic nervous systems.⁴⁰ Neurons that orchestrate emesis are located throughout the medulla and organized by a central pattern generator (CPG) that coordinates the sequence of events leading to emesis. The CPG receives input from the area postrema and abdominal vagal afferents. Anti-emetic drugs antagonize neurotransmitters (Figure 1⁴⁰) that orchestrate the progression of nausea to vomiting. Commonly used anti-emetics antagonize the following receptors: muscarinic acetylcholine (mR), dopamine (D_2) , serotonin (5-HT₃), histamine (H_1) and neurokinin (NK_1) . Both ondansetron and mirtazapine are serotonin (5HT₃) receptor antagonists⁴⁰ which prevent vagal afferent signaling to the hindbrain; however, mirtazapine offers three additional sites of action to impede the emetic process (Figure 1⁴⁰): 1) histamine (H_1R) , which has input directly to the vomiting center; 2) muscarinic (mR) which also has input directly into the vomiting center; and 3) central presynaptic adrenergic α_2 (adrenergic $\alpha_2 R$), which activates emesis.

Figure 1. Neurotransmitters involved in emesis and sites of action: $\alpha_2 \mathbf{R}$ =adrenergic α_2 -receptor; CPG=central pattern generator; $D_2 \mathbf{R}$ =dopamine 2receptor; Δ^9 -THC= Δ 9-tetra-hydrocannabinol; DVC=dorsal vagal complex; **5-HT**=serotonin; **H**=histamine; NK=neurokinin; **m**R=muscarinic; mirtazapine's action indicated by arrows at receptor sites that are bolded below and arrows are receptor site.

STUDY ENDPOINTS:

The primary outcome is the change in PUQE (Pregnancy Unique Quality of Emesis)⁴³ score. Secondary outcomes include: (1) Self-administered Comorbidity Questionnaire, (2) NIH PROMIS Global Health scale, (3) Patient Health Questionnaire-9 (depression scale), (4) Generalized Anxiety Disorder-7 scale, (5) Asberg Side Effects. Plasma will be obtained for quantitation of mirtazapine concentrations at each assessment during mirtazapine treatment. DNA will be obtained to explore whether pregnant persons who are most (or least) likely to benefit from treatment can be identified through pharmacogenetics.

STUDY INTERVENTION(S) / INVESTIGATIONAL AGENT(S):

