	Not at all (1) 7 or more times (5) No time	Not at all (1) 1 hour or less (2) 7 or more times (5) 5-6 times (4) No time 1-2 times	Not at all (1)1 hour or less (2)2-3 hours (3)7 or more times (5)5-6 times (4)3-4 times (3)No time1-2 times3-4 times	Not at all (1)1 hour or less (2)2-3 hours (3)4-6 hours (4)7 or more times (5)5-6 times (4)3-4 times (3)1-2 times (2)No time1-2 times (4)3-4 times5-6 times			

sNVP Assessment. The Pregnancy Unique Quality of Emesis PUQE-24)(Figure 2)⁴³ was used in studies submitted for FDA approval of Diclegis® (doxylamine/ pyridoxine).⁴⁴ Subjects will record their PUQE score daily (for prior 24 hours) to track symptom change in a secure on-line REDCap system.

Participants. Subjects with clinically significant NVP will be recruited. An

initial score of 10 or more (high moderate/severe NVP) on the PUQE⁴³ scale is required. We include the criterion from the study¹² that showed the association of sNVP with developmental deficits (with weight loss, defined as 5% loss from pre-pregnancy). Pregnant persons will be recruited from in- and out-patient practices and the Obstetrical Triage Service, where Co-I's Drs. [name] and [name] provide care, and from our academic obstetrical practices. Upon referral, a research coordinator will contact the participant's obstetrician, and meet with the participant to review eligibility criteria, the study procedures, and obtain written consent.

Intake Days 1	c	1, N dose		aza	pin																	
Davs 1	-	lose	 													Week 3, Mirtazapine ODT dose =						
Davs 1				15	5 mg	9		30 mg									45	mg				
,-	2	3	4	5	6	7 Visit	8	9	10	11	12	13	14 Visit	15	16	17	18	19	20	21 Visit		
GA, CQ; ECG; Medical Review																				ECG		
						DNA, Plasma							Plasma							Plasma		
Wt, Ht, BP						Wt; BP							Wt; BP							Wt; BP		
$\begin{array}{c} PUQE \rightarrow \\ GH \end{array}$	\rightarrow	\rightarrow	\rightarrow	\rightarrow	\rightarrow	PUQE GH	\rightarrow	\rightarrow	\rightarrow	\rightarrow	\rightarrow	\rightarrow	PUQE GH	\rightarrow	\rightarrow	\rightarrow	\rightarrow	\rightarrow	\rightarrow	PUQE GH		
PHQ-9 GAD-7 C-SSRS						PHQ-9 GAD-7 C-SSRS							PHQ-9 GAD-7 C-SSRS							PHQ-9 GAD-7 C-SSRS		
ASE SS	ASE SS					ASE SS		ASE SS					ASE SS		ASE SS					ASE SS		

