Authorized research personnel will work with clinicians from the Northwestern Obstetrics and Gynecology services and the Obstetrical Triage program to identify potentially eligible individuals and approach them about their interest in participating. We have defined several eligibility criteria to allow participants to be screened by our study team. Subject burden can be reduced and study efficiency improved by asking only those subjects likely to be eligible to undergo a full baseline assessment. The screen includes: 1) age 2) gestational age of the fetus, 3) confirmation of plan to receive care and deliver at Prentice Women's Hospital (PWH), 4)

PUQE score of 10-15, 5) has been treated with at least two anti-emetic/antinauseant drugs with inadequate response; and 8) English speaking.

The inclusion/exclusion criteria will be reviewed in the patient's chart and documented on the screening log. If a patient meets all the inclusion criteria for enrollment, does not have any of the exclusion criteria, she will be approached about the study by authorized personnel. Her primary obstetrician will be contacted to review the patient's participation.

Brochures will be available to provide potential subjects with additional information. We will also post information about this study on our Asher Center and Northwestern Medicine websites, as well as post on the NCT site.

COMPENSATION FOR PARTICIPATION IN RESEARCH ACTIVITIES

Participants will be compensated with \$35 for each week of the three-week trial. If a participant wishes to participate in the continuation period or a mirtazapine tapering regimen, they will continue for 5 additional weeks and compensated with \$35 each week.

If a participant enters into the study early in pregnancy (gestational age of 5 weeks), they will have monthly visits after the 8 weeks is completed, for a maximum total of 10 visits.

Compensation will be provided in a form of a check at the end of each week during their followup visit.

WITHDRAWAL OF PARTICIPANTS

A participant will be withdrawn from the research without their consent if there is: 1) refusal to follow the medication protocol, and/or 2) refusal to answer study questionnaires, 3) the participant fails to respond to contact attempts from the study team.

RISKS TO PARTICIPANTS

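### The SAP's 2.3-point detectable PUQE change does not follow from its stated 80% power: the same inputs give about 2.0 points, and 2.3 points has about 91% power

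*SAP*

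**What the plan says.** The calculation is in one paragraph of the SAP, Sample Size Considerations. Its inputs are given as "we will assume 80% power, two-sided significance=.05, and a standard deviation of 2.1" for the PUQE score, taken from a published placebo-controlled trial of doxylamine and pyridoxine, with an entry score of about 10. The standard deviation of the change from baseline to week 3 is "estimated to be 2.97 by assuming that the correlation is zero". The result is: "With 20 subjects, we can detect a 23% reduction in mean symptom scores (a 2.3 point decrease in PUQE scores"). Enrolment is then set at 25 to allow for 20% dropout. No statistical test is named for this calculation.

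The same section limits the claim: "The proposed study is not powered nor expected to evaluate the efficacy of mirtazapine for sNVP". The SAP's Analytic Approach makes a similar disclaimer for the outcomes generally.

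The protocol, under Study Endpoints, says "The primary outcome is the change in PUQE" score. For eligibility, the Participants paragraph under Procedures Involved requires an "initial score of 10 or more (high moderate/severe NVP) on the PUQE" scale, and Figure 6 (Inclusion and Exclusion Criteria) lists "PUQE score of 10-15; moderate/high or severe". The screen under Recruitment Methods uses the same 10 to 15 range.

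**The concern.** Power, significance level, standard deviation of change and sample size together fix the detectable change. All four are stated, so the 2.3 points should be reproducible. The two neighbouring figures, 2.97 and 25, do reproduce; the detectable change does not.

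This is the only statistical calculation offered for 20 completers and 25 enrolled, and it concerns the outcome that the protocol calls primary. The protocol's Objectives also say that the study will inform sample size estimation for a later randomised trial, so the power statement may be reused. A reader who takes it at face value would believe that 20 completers have 80% power for 2.3 points, which understates the power.

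A smaller point concerns the percentage. The 23% divides 2.3 by an entry score of 10, and nobody may enter with a score below 10.

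**Working it through.** **Inputs (SAP, Sample Size Considerations):** n = 20 completers; standard deviation of one score 2.1; correlation 0; two-sided significance level 0.05; power 80%. **Assumption:** a paired t-test (a one-sample test on the changes). The protocol describes an open trial with no control group, and the SAP supplies a standard deviation of change.

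**1. Figures that reproduce.**
- Standard deviation of change: √(2 × 2.1² × (1 − 0)) = 2.1 × √2 = 2.97.
- Enrolment: 20 / (1 − 0.20) = 25.
- Percentage, given an entry score of 10: 2.3 / 10 = 23%.

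**2. Detectable change at the stated 80% power.** The standard error of the mean change is 2.97 / √20 = 0.664.
- Normal approximation: (1.960 + 0.842) × 0.664 = 1.86 points.
- Exact, from the noncentral t distribution with 19 degrees of freedom: 1.96 points.

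The stated 2.3 is 2.3 / 1.96 = 1.17 times the exact value.

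**3. Power for 2.3 points with n = 20.** The noncentrality is 2.3 / 0.664 = 3.46.
- Normal approximation: Φ(3.46 − 1.96) = 93.4%.
- Exact: 90.7%.
- Rounding does not explain the gap: changes of 2.25 and 2.35 points have 89.5% and 91.8% power.

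**4. Sample size for 2.3 points at 80% power.** The exact power is 79.6% with n = 15 and 82.5% with n = 16, so 16 completers suffice.

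**5. Could another reading give 2.3?** In each row the inputs not mentioned are as stated in the SAP.

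| Variant | Detectable change (points) |
|---|---|
| One-sided 0.05 | 1.71 |
| Two-sided 0.025 | 2.20 |
| Two-sided 0.01 | 2.49 |
| Wilcoxon signed-rank, relative efficiency 0.955 to 0.864 | 2.01 to 2.13 |
| Two-sample, 10 or 20 per arm, SD 2.1 or 2.97 | 1.86 to 3.94, none equal to 2.3 |
| Correlation 0.25 | 1.70 |
| Correlation 0.50 | 1.39 |
| Power 85% | 2.10 |
| Power 90% | 2.27 |

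With n = 20 and 80% power, 2.3 points would need a standard deviation of change of 3.48. With 2.1 at each visit, that implies a correlation of 1 − 3.48² / (2 × 2.1²) = 1 − 12.1 / 8.82, or about −0.38; the SAP states zero. Keeping n, the standard deviation and the two-sided 0.05 level, the variant that rounds to 2.3 is 90% power.

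**6. The percentage.** With eligibility at 10 to 15, a mean of exactly 10 would require every participant to enter at 10. The documents give no other entry mean. For assumed means of 11 and 12.5, 2.3 points is 2.3 / 11 = 20.9% and 2.3 / 12.5 = 18.4%.

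**The case against.** The strongest objection is that nothing depends on the number. The SAP reports that the study closed after two participants, so neither 2.0 nor 2.3 points describes what the data can show, and no enrolment decision remains. The SAP disclaims efficacy power twice and calls the calculation preliminary. The target of 25 also reflects what the grant mechanism and an accrual of one or two subjects a month could deliver. All of this stands, and it keeps the point minor.

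A second objection is that the sentence is not literally false: 20 subjects do detect 2.3 points with at least 80% power. That is true. But the sentence reports the result of a calculation for which 80% power is stated, so a reader will take 2.3 as the 80% value, and it is not.

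Third, the test is my assumption. This is fair, and the sponsor should supply the test actually used. However, none of the alternative tests tried gives 2.3 points at the stated power, significance level, sample size and standard deviation.

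Fourth, 23% follows exactly from the stated entry score of about 10, and the means of 11 and 12.5 are mine. This also stands. The percentage is a question about a planning assumption, separate from the arithmetic error.

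**Conclusion.** The concern holds, as a minor one. Under a paired t-test, the stated inputs give a detectable change of 1.96 points at 80% power. The 2.3 points has 90.7% power, 10.7 percentage points above the stated level, and at 80% power it needs 16 completers where the SAP uses 20. A calculation at 90% power reported as 80% would explain the figure, but the documents cannot confirm that.

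The error is conservative: the planned 20 completers were more than enough for 2.3 points at 80% power. The conclusion rests on the SAP's own standard deviation and zero correlation; a positive correlation would widen the gap.

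**What to change.** Correct the sentence in Sample Size Considerations, for example:

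> Twenty completers give 80% power for a mean PUQE change of 2.0 points (about 91% power for 2.3 points), using a paired t-test at two-sided 0.05 with a standard deviation of change of 2.97.

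If 90% was the intended power, change 80% to 90% and keep 2.3 points. In either case the sponsor should confirm the test. Express the effect in points, or as a percentage of an entry mean compatible with PUQE 10 to 15.

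The cost is one sentence. The target of 25 and the planned analyses stay as they are. Because the study has closed, this corrects the record and guards against reuse of the figure in planning the later trial.

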Side Effect Assessment, Before mirtazapine treatment, a comprehensive metabolic profile and urinalysis will be obtained as standard of care. An ECG also will be performed. The degree of QT prolongation observed with both 45 mg (therapeutic) and 75 mg (supra-therapeutic) doses of mirtazapine was not clinically meaningful,⁴⁷ and QTc ≥500 msec was not observed among mirtazapine-treated patients.⁵⁰ The drug regimen to which mirtazapine may be added will be reviewed by [name], a fellowship-trained clinical pharmacologist and obstetrician, for QTc prolongation risk prior to mirtazapine administration, or [name], an attending obstetriciangynecologist in Obstetrical Triage, or [name], the PI, a perinatal psychopharmacologist. Side effects will be assessed with the 14-item Asberg Side Effects (ASE)⁵¹ scale, which was adapted by our team for SSRI-treated pregnant persons.^{52,53} The ASE guantifies discomforts from mild to severe and a summary of overall distress. Serotonin hyper-stimulation will be reviewed with Hunter's Decision Rules for Diagnosis of Serotonin Toxicity (SS).⁵⁴ SS is characterized by tachycardia, diaphoresis, myoclonus and tremor.⁵⁵ The incidence of SS is infrequent (9/10,000) as shown in a retrospective cohort study⁵⁶; however, ondansetron, metoclopramide and mirtazapine have been associated with SS during monotherapy and with other serotonergic drugs⁵⁷, although rarely in young persons.⁵⁸ Treatment includes drug discontinuation, benzodiazepines and the anti-serotonergic drug cyproheptadine.

Specific Instrument Use

Pregnancy Unique Quality of Emesis (PUQE)⁴³ **scale (Figure 2):** We will utilize the PUQE scale to capture the severity of nausea and vomiting in pregnancy based on three physical symptoms: nausea, vomiting, and retching over the previous 24 hours. A PUQE score of < 6 is considered mild, a score from 7-12 is moderate, and a score of 13+ is considered severe. This scale will be entered daily in REDCap directly by the participant.

Self-Administered Comorbidity Questionnaire (SCQ)⁵⁹**:** The Comorbidity Questionnaire (CQ) assesses comorbid conditions in clinical and health services research. The questionnaire is self-administered, short, easily understood, and can be completed by individuals without any medical background. It also allows the subject to note the severity of each comorbid conditions and their perception of its impact on their function.

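### The 23% detectable reduction divides by a PUQE of 10, the lowest eligible score, so it is the upper limit of the relative figure and not its expected value

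*SAP*

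**What the plan says.** The SAP, Sample Size Considerations, sets out these assumptions: "we will assume 80% power, two-sided significance=.05"; "a standard deviation of 2.1", taken from a published placebo-controlled trial of another antiemetic; and "a moderately severe PUQE score (\approx 10) at study entry". The SD of the change to week 3 is "conservatively estimated to be 2.97 by assuming that the correlation is zero". The result is "With 20 subjects, we can detect a 23% reduction in mean symptom scores (a 2.3 point decrease in PUQE scores". Allowing for 20% dropout, 25 are to be enrolled. The same section calls the sample size preliminary and says the study is not powered for efficacy.

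The protocol limits who can enter. Figure 6 (Inclusion and Exclusion Criteria) requires "PUQE score of 10-15; moderate/high or severe". The Participants paragraph under Procedures Involved sets a minimum of 10, and the screening list under Recruitment Methods repeats 10 to 15. On the scale itself, Specific Instrument Use states that "a score from 7-12 is moderate, and a score of 13+ is considered severe".

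**The concern.** The SAP does not call 10 a mean, but it uses it as one: 2.3 / 0.23 = 10. A mean can equal the lowest admissible value only if nobody scores above it. Every other eligible entry mean is higher, so the percentage that goes with a given number of points can only fall. The approximation therefore errs in one direction.

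Change in PUQE is the protocol's primary outcome, 23% is the only relative effect in the plan, and the study is meant to inform the sample size of a later RCT. At an entry mean above 10, the two halves of the stated figure stop being the same effect. At a mean of 12.5, for example, 23% is 0.23 x 12.5 = 2.9 points, not 2.3. Someone reusing the percentage and someone reusing the points would be working with different targets.

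**Working it through.** **Inputs.** From the SAP, Sample Size Considerations: single-time-point SD 2.1; SD of change 2.97; n = 20 evaluable; 80% power; two-sided 0.05; entry PUQE about 10; 20% dropout. From Protocol Figure 6: eligible PUQE 10 to 15. The documents give no expected entry mean, so results are shown over a range.

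**1. The plan's own figures.**
- SD of change with correlation 0: 2.1 x sqrt(2) = 2.97. Reproduces.
- Enrolment: 20 / (1 - 0.20) = 25. Reproduces.
- Percentage: 2.3 / 10 = 23%. The division is correct; the denominator is the issue.
- Points: the normal approximation gives (1.960 + 0.842) x 2.97 / sqrt(20) = 2.80 x 0.664 = 1.86. The paired t-test (noncentral t, 19 df) gives 1.96. Neither is 2.3. At 2.3 points the paired t-test has power 0.907, and 80% power would need only 16 subjects. At 90% power the detectable difference with n = 20 is 2.27, which does match 2.3.

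**2. Which entry means the SAP's SD allows.** For scores between 10 and 15 with mean m, the variance cannot exceed (m - 10)(15 - m).
- At m = 10 the bound is 0, so the baseline SD would be 0.
- For SD 2.1, (m - 10)(15 - m) must be at least 2.1^2 = 4.41, that is, m^2 - 25m + 154.41 <= 0.
- Hence m = (25 ± sqrt(625 - 617.64)) / 2 = (25 ± 2.71) / 2, or about 11.1 to 13.9.

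An entry mean of 10, an entry SD of 2.1 and the 10 to 15 rule therefore cannot all hold.

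**3. The percentage over that range.** 2.3 / 11.14 = 20.6% and 2.3 / 13.86 = 16.6%. For the 80%-power value, 1.96 / 11.14 = 17.6% and 1.96 / 13.86 = 14.1%.

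Across the eligible range, holding the SD of change at 2.97:

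| Entry mean | 2.3 points as % | 1.96 points as % | Power for a true 23% reduction (n = 20) |
|---|---|---|---|
| 10 | 23.0 | 19.6 | 0.907 |
| 11 | 20.9 | 17.8 | 0.951 |
| 12 | 19.2 | 16.3 | 0.976 |
| 12.5 | 18.4 | 15.7 | 0.984 |
| 13 | 17.7 | 15.1 | 0.989 |
| 15 | 15.3 | 13.1 | 0.998 |

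A mean of 11 meets the eligibility rule but is just short of the range in step 2: its largest possible SD is sqrt(1 x 4) = 2.0.

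**4. What does not move.** The detectable difference in points comes from the SD of change, n, alpha and power. The entry mean does not enter it, so n = 20 and enrolment of 25 are unaffected.

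**The case against.** The strongest reply is that this is a rough label on a figure already given in points. The SAP writes 10 as an approximation, and its next sentence states its expectation in points only. No analysis in the SAP compares an observed percentage with 23%. The section disclaims efficacy power, and it records that the study closed after 2 participants. The direction is also harmless, since a higher entry mean makes a true 23% reduction easier to detect.

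Most of this stands, and it keeps the point small. It does not rescue the percentage: the approximation can err only one way, and it conflicts with the SD in the same paragraph.

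Several stronger readings are tempting, and the documents do not support them:

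- *The figure describes nobody who can be enrolled.* A score of 10 is eligible. The figure sits at the edge of the admissible range, not outside it.
- *A mean of 10 is a moderate population in a trial of severe disease.* Figure 6 expressly admits upper-moderate scores, and the protocol's Objectives define severe NVP by 5% weight loss or persistence beyond 20 weeks, not by a PUQE of 13 or more.
- *The RCT will inherit the 23%, or the result will be judged to have missed a planned effect.* The plan says neither. The 23% is a detectable effect, and the SAP anticipates a larger reduction than 2.3 points.
- *The entry mean can be estimated by truncating an assumed source population at 10.* The documents give no source mean. Truncation would also shrink the baseline SD, so the result could not be combined with a points figure based on SD 2.1.

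**Conclusion.** The point holds as an internal inconsistency of low weight. For 2.3 points, 23% is the largest relative reduction the eligibility rule permits. Under the SAP's own SD the corresponding figure is about 16.6% to 20.6%, an overstatement of roughly 2 to 6 percentage points. The error is conservative and confined to the percentage.

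Changing the denominator alone would still leave an unreproducible figure, because 2.3 points does not follow from 80% power and the SAP's other inputs; 1.96 does.

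The conclusion assumes that 10 serves as the entry mean (implied by 2.3 / 0.23), that entry scores stay within 10 to 15, and that SD 2.1 applies at entry as the 2.97 calculation requires. It also keeps the SD of change at 2.97. If the restricted range lowered the baseline SD to 1.0 to 1.7, with follow-up SD 2.1 and correlation 0, the detectable difference at 80% power would itself fall to about 1.5 to 1.8 points. That again makes the plan cautious, not optimistic.

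**What to change.** In the SAP, Sample Size Considerations:

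1. State the detectable difference in points with its test and power. For a paired t-test with n = 20, SD of change 2.97 and two-sided 0.05, that is 1.96 points at 80% power; if 2.3 points is kept, give the power as about 90%.
2. Either drop the percentage, or give it over entry means allowed by the 10 to 15 criterion and label those means as assumptions. For 1.96 points, examples are 17.8% at a mean of 11 and 15.7% at 12.5, noting that 11 lies just below what SD 2.1 allows.
3. Replace the entry score of about 10 with a mean consistent with both the eligibility rule and the assumed SD: about 11.1 to 13.9 if SD 2.1 is retained.

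This costs a few lines of SAP text and changes nothing in enrolment, eligibility or data collection. As the study has closed, the benefit is an accurate record for anyone who reuses the figure.
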